## **21.7. Efficacy Endpoints**

Analysis of clinical assessments and potential progression or disease will be explored. Comparisons between LYT-100 and placebo will be based on clinical interpretation of effect, magnitudes of effect, and a preponderance of evidence. Estimates of changes over time from these data may be used to power future clinical studies.

Lymphatic obstructions and subsequent edema will be measured using each of the following metrics:

- Limb water content (BIS)
- Limb volume (truncated cone tape measure and/or perometry)
- Tissue dielectric constant (MoistureMeterD)
- Tissue firmness (tonometry/SkinFibroMeter)

For each of these metrics, use of a mixed model for repeated measures (MMRM) will be used to provide model-based estimates of changes over time in each of these outcomes. Descriptive statistics will also be provided at each time point. Details for the model (including covariates to be included) will be provided in the SAP.

The number of occurrences of cellulitis and lymphangitis within the treatment period will be tabulated.

Visual analog scales for pain, swelling, discomfort, and function, and QoL assessments using the LYMPH-Q ([Appendix 2](#)) and LYMQOL ([Appendix 3](#)) questionnaires will be provided at baseline and treatment period timepoints. Both an MMRM and descriptive statistics will be used to describe the outcomes over time, considering each of their respective domains as listed in [Section 17](#).

## **22. ETHICS**

### **22.1. Ethics Review**

The final study protocol, including the final version of the ICF, must be approved or given a favorable opinion in writing by an IRB/IEC as appropriate. The Investigator must submit written approval to the Sponsor before they can enroll any patient into the study.

The Investigator is responsible for informing the IRB/IEC of any amendment to the protocol in accordance with local requirements. In addition, the IRB/IEC must approve all advertising used to recruit patients for the study. The protocol must be re-approved by the IRB/IEC upon receipt of amendments and annually, as local regulations require.

The Investigator is also responsible for providing the IRB/IEC with reports of any reportable serious adverse drug reactions from any other study conducted with the study drug (active). The Sponsor will provide this information to the Investigator.

Progress reports and notifications of serious adverse drug reactions will be provided to the IRB/IEC according to local regulations and guidelines.

### **22.2. Ethical Conduct of the Study**

The study will be performed in accordance with ethical principles that have their origin in the Declaration of Helsinki and are consistent with ICH GCP applicable regulatory requirements and the Sponsor's policy on Bioethics.

### **22.3. Written Informed Consent**

The Investigator will ensure that the patient is given full and adequate oral and written information about the nature, purpose, possible risk, and benefit of the study. Patients must also be notified that they are free to discontinue from the study at any time without prejudice. The patient should be given the opportunity to ask questions and allowed time to consider the information provided before voluntarily signing the written ICF.

The patient's signed and dated informed consent must be obtained before conducting any study procedures. The patients will be informed of their rights to privacy but will be made aware that the study data will be submitted to the Sponsor and possibly to drug regulatory authorities for review and evaluation. They will be informed also that the study monitor may inspect their medical records to verify the accuracy and completeness of the study records and results.

The acquisition of informed consent should be documented in the patient's medical records, as required by the Integrated Addendum to ICH E6(R1): Guideline for Good Clinical Practice ICH E6(R2), and the ICF will be signed and personally dated by the patient and by the person who conducted the informed consent discussion.

The Investigator must maintain the original, signed ICF. A copy of the signed ICF must be given to the patient or legal representative. The date that informed consent was signed will be recorded on the eCRF.

## **22.4. Data Protection**

Patients will be informed that data will be held on file by the Sponsor and that these data may be viewed by staff including the study monitor and by external auditors on behalf of the Sponsor and appropriate regulatory authorities. Patients will also be informed that a study report will be prepared and may be submitted to regulatory authorities and for publication. However, patients will be identified in such reports only by study identification number, gender, and age. All patient data will be held in strict confidence.

## **23. REGULATORY REQUIREMENTS**

The Sponsor will fulfill the obligations that their role entails. Aside from approval by the IRB/IEC, no other regulatory approval will be required.

The Sponsor will file the protocol to an Investigation New Drug following all US FDA requirements.

## **24. DATA HANDLING AND RECORDKEEPING**

### **24.1. Inspection of Records**

The Sponsor will be allowed to conduct site visits to the investigation facilities for the purpose of monitoring any aspect of the study. The Investigator agrees to allow the monitor to inspect the drug storage area, study drug stocks, drug accountability records, patient charts and study source documents, and other records relative to study conduct.

### **24.2. Retention of Records**

All source data, clinical records and laboratory data relating to the study will be archived for 15 years after the completion of the study. All data will be available for retrospective review or audit.

Source documents are original documents, data, and records from which the patient's eCRF data are obtained. These include but are not limited to hospital records, clinical and office charts, laboratory and pharmacy records, diaries, microfiches, radiographs, angiograms, study drug accountability logs, and correspondence.

The Investigator and study staff are responsible for maintaining a comprehensive filing system of all study-related (essential) documentation. These include but are not limited to: IRB/IEC correspondence, study drug accountability logs, and curricula vitae of all personnel participating in the study. These files must be suitable for inspection at any time by the Sponsor, monitor, and/or applicable regulatory authorities. All essential documentation should be retained by the institution for 15 years.

No study document should be destroyed without prior written agreement between the Sponsor and the Investigator. If the Investigator wishes to assign the study records to another party or move them to another location, they must notify the Sponsor in writing of the new responsible person and/or the new location.

### **24.3. Liability/Indemnity/Insurance**

The Sponsor will ensure sufficient insurance is available to enable it to indemnify and hold the Investigator(s) and relevant staff as well as any hospital, institution, ethics committee or the like, harmless from any claims for damages for unexpected injuries, including death, that may be caused by the study drug, but only to the extent that the claim is not caused by the fault or negligence of the patients or Investigator(s).

## **25. PUBLICATION POLICY**

### **25.1. Publication of Results**

The publication, presentation, or other public disclosure of study results (each, a “Publication”) will be accurate and honest, undertaken with integrity and transparency and in accordance with the Sponsor’s approval.

Publication of results will be subjected to fair peer-review. Authorship will be discussed between researchers prior to study commencement (or as soon as possible thereafter) and reviewed whenever there are changes in participation.

Acknowledgment will be given to collaborating institutions and hospitals and other individuals and organizations providing finance or facilities. Patient confidentiality will be maintained by referring to individual patients by their identifying code used in the trial. Data will not be released publicly until the manuscript is accepted for publication. In the case of no publication, information will only be released to the public and media in accordance with the Sponsor’s approval.

Study data that have not been published, presented, or otherwise disclosed in accordance with the clinical trial agreement shall remain confidential information of the Sponsor, the Investigator may not disclose or permit the disclosure of such unpublished data to any third party, nor may they disclose or permit the disclosure of any study data to any third party in greater detail than the same have been disclosed in any permitted publication, presentation, or other disclosure.

The clinical trial will be posted to the Clinicaltrials.gov registry as required by legal agreement, local law, or regulation.

### **25.2. Disclosure and Confidentiality**

By signing this protocol, the Investigator agrees to keep all information provided by the Sponsor in strict confidence and to request similar confidentiality from their staff and the IRB/IEC. Study documents provided by the Sponsor (Protocols, IBs, eCRFs, etc.) will be stored appropriately to ensure their confidentiality. The information provided by the Sponsor to the Investigator may not be disclosed to others without direct written authorization from the Sponsor, except to the extent necessary to obtain informed consent from patients who wish to participate in the study.

The Investigator must ensure that the patient’s anonymity is also maintained. Patients should only be identified by their initials and a patient study number on the eCRFs and other source documents. Other study-related documents (e.g., signed ICFs) should be kept in strict confidence by the Investigator.

## **26. QUALITY CONTROL AND QUALITY ASSURANCE**

### **26.1. Compliance with Good Clinical Practice**

To ensure compliance with GCP and all applicable regulatory requirements, the Sponsor may conduct a quality assurance audit. Please see Section 20.3 for more details regarding the audit process.

The study will be carried out in accordance with the current version of the Declaration of Helsinki (Ethical Principles for Medical Research Involving Human Subjects), Integrated Addendum to ICH E6(R1): Guideline for GCP ICH E6(R2), and the applicable local regulations.

### **26.2. Archiving and Regulatory Inspection**

All study-related documents and records are to be retained for a minimum of 15 years after trial completion. Written agreement from the Sponsor must precede destruction of the same.

In accordance with ICH GCP, this study may be selected for audit. Inspection of site facilities (e.g., pharmacy, medication storage areas, laboratories) and review of study-related records may occur by the Sponsor, the Sponsor's representative(s), or regulatory authority to evaluate the study conduct and compliance with the protocol, ICH GCP, and applicable regulatory requirements.

## **27. SPONSOR AND INVESTIGATOR OBLIGATIONS**

### **27.1. Protocol Amendments**

Neither the Investigator nor the Sponsor will modify or alter this protocol without the agreement of the other. All agreed protocol amendments will be clearly recorded on a protocol amendment form and will be signed and dated by the original protocol approving signatories. All protocol amendments will be submitted to the relevant IRB/IEC for approval before implementation, as required by local regulations. The only exception will be when the amendment is necessary to eliminate an immediate hazard to the trial patients. In this case, the necessary action will be taken first, with the relevant protocol amendment following shortly thereafter.

### **27.2. Protocol Deviations**

Should any protocol deviation occur, it must be reported to the study monitor as soon as is reasonably practical. The deviation and the reason for its occurrence must be documented, reported to the relevant IRB/IEC (if required) and included in the clinical study report.

## APPENDIX 1: Blood Volumes

**Table 11: Estimated Blood Volumes**

Test	Per Test Volume	Total Number of Samples	Total Volume
CYP1A2, CYP2C9, CYP2C19, and CYP2D6 genotyping	4 mL	1	4 mL
Pregnancy test and/or FSH (as applicable)	4 mL	1	4 mL
Hematology	3 mL	6	18 mL
Blood chemistry	5 mL	10	50 mL
Coagulation	4 mL	6	24 mL
PK	4 mL	8	32 mL
Fibrotic and inflammatory biomarkers	4 mL	5	20 mL
Overall Blood Volume Collected Per Patient			152 mL

Abbreviations: FSH = Follicle-stimulating hormone; PK = Pharmacokinetics.

## APPENDIX 2: LYMPH-Q—Upper Extremity Module

### LYMPH-Q UPPER EXTREMITY: SYMPTOMS

How does your arm feel (symptoms)?

**NOTE: If your breast cancer surgery affected both of your arms, answer each question thinking about the arm that bothers you the most.**

**Please answer thinking of the PAST WEEK. Please rate the severity of each of these symptoms:**

	Severe	Moderate	Mild	None
1. Pain when your arm is touched ?	1	2	3	4
2. Pain when your arm is at rest ?	1	2	3	4
3. Arm feeling hotter or colder than normal?	1	2	3	4
4. Arm feeling stiff?	1	2	3	4
5. Arm symptoms disturbing your sleep (eg, pain, swelling)?	1	2	3	4
6. Aching feeling in your arm?				
7. Arm feeling numb?	1	2	3	4
8. Pressure in your arm?	1	2	3	4
9. Pain when you move your arm?	1	2	3	4
10. Clumsiness (eg, dropping or spilling things)?	1	2	3	4
11. Tingling in your arm (ie, pins and needles feeling)?	1	2	3	4
12. Arm feeling tired?	1	2	3	4
13. Arm feeling weak (ie, lack of strength)?	1	2	3	4

14.Arm feeling heavy?	1	2	3	4
15.Arm swelling?	1	2	3	4

## LYMPH-Q UPPER EXTREMITY: FUNCTION

How difficult is it for you to use your arm with lymphedema?

	Extremely difficult	Moderately difficult	A little difficult	Not at all difficult
1. Putting on or taking off clothes?	1	2	3	4
2. Washing your hair?	1	2	3	4
3. Buttoning a shirt or coat?	1	2	3	4
4. Holding a phone to your ear?	1	2	3	4
5. Reaching across yourself (eg, to put on a car seatbelt)?	1	2	3	4
6. Gripping a handle (eg, tennis racket, broom)?	1	2	3	4
7. Holding a book to read?	1	2	3	4
8. Using your hand and fingers (eg, type, write)?	1	2	3	4
9. Reaching for an object overhead?	1	2	3	4
10. Holding a bag of groceries?	1	2	3	4
11. Doing household chores that use your arm (eg, vacuum, make bed)?	1	2	3	4
12. Doing physical activities that involve moving your arm (eg, throw a ball, tennis, gardening)?	1	2	3	4

## LYMPH-Q UPPER EXTREMITY: PSYCHOLOGICAL

Does lymphedema in your arm(s) affect how you feel?

Please answer thinking of the PAST WEEK. With your arm lymphedema in mind, how often have you felt:

	Always	Often	Sometimes	Never
1. Desperate?	1	2	3	4
2. Hopeless?	1	2	3	4
3. Angry?	1	2	3	4
4. Depressed?	1	2	3	4
5. Stressed?	1	2	3	4
6. Afraid?	1	2	3	4
7. Anxious?	1	2	3	4
8. Fed-up?	1	2	3	4
9. Unattractive?	1	2	3	4
10. Worried?	1	2	3	4
11. Irritated?	1	2	3	4
12. Frustrated?	1	2	3	4

## APPENDIX 3: Lymphedema Quality of Life Tool, Arm (Sample)

The score for the individual responses are given below. If the item is not scored and left blank or not applicable this is scored with a 0. Domain totals are calculated by adding the individual scores and dividing the total by the number of questions answered. (If >50% of questions per domain are not answered this cannot be calculated and =0).

The four domains and their corresponding questions are: Function I (a–h), 2, 3;  
Appearance 4, 5, 6, 7, 8; Symptoms 9, 10, 11, 12, 13, 14; and Mood 15, 16, 17, 18, 19, 20.  
Overall quality of life (Q21) is scored as the value marked by the patient, between 0–10.

(1) How much does your swollen arm affect the following daily activities?				
	Not at all	A little	Quite a bit	A lot
a) occupation	1	2	3	4
b) housework	1	2	3	4
c) combing hair	1	2	3	4
d) dressing	1	2	3	4
e) writing	1	2	3	4
f) eating	1	2	3	4
g) washing	1	2	3	4
h) cleaning teeth	1	2	3	4
(2) How much does it affect your leisure activities/social life?				
	1	2	3	4

Please give example(s) of this.

.....

.....

(3) How much do you have to depend on other people?	1	2	3	4
(4) How much do you feel the swelling affects your appearance?	1	2	3	4
(5) How much difficulty do you have finding clothes to fit?	1	2	3	4
(6) How much difficulty do you have finding clothes you would like to wear?	1	2	3	4
(7) Does the swelling affect how you feel about yourself?	1	2	3	4
(8) Does it affect your relationships with other people?	1	2	3	4
(9) Does your lymphoedema cause you pain?	1	2	3	4
(10) Do you have any numbness in your swollen arm?	1	2	3	4
(11) Do you have any feelings of 'pins and needles' or tingling in your swollen arm?	1	2	3	4
(12) Does your swollen arm feel weak?	1	2	3	4
(13) Does your swollen arm feel heavy?	1	2	3	4
(14) Do you feel tired?	1	2	3	4
In the past week	1	2	3	4
(15) Have you had trouble sleeping?	1	2	3	4
(16) Have you had difficulty concentrating on things, e.g. reading?	1	2	3	4
(17) Have you felt tense?	1	2	3	4
(18) Have you felt worried?	1	2	3	4
(19) Have you felt irritable?	1	2	3	4
(20) Have you felt depressed?	1	2	3	4
(21) (24) Overall, how would you rate your quality of life at present? Please mark your score on the following scale:	1	2	3	4

Poor	0	1	2	3	4	5	6	7	8	9	10	Excellent
------	---	---	---	---	---	---	---	---	---	---	----	-----------

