- LYMPH-Q ([Appendix 2](#)): This is a patient completed questionnaire that measures the degree of symptoms, function, and psychological impact with patients who have upper extremity lymphedema. Symptoms are rated on a 15-item scale (severe, moderate, mild to none) to measure how the arm feels, the function portion is measured on a 12-item scale (extremely difficult, moderately difficult, a little difficult and not at all difficult) to determine arm function capability, and the psychological portion is measured on a 12-item scale (always, often, sometimes, never) to evaluate how a patient feels having lymphedema.
- LYMQOL ([Appendix 3](#)): This is a patient completed questionnaire that assesses upper limb lymphedema and symptoms, and ability to perform common functional

activities in patients with BCRL. It addresses the following four domains – Symptoms, Body Image/Appearance, Function, and Mood. Each item is scored as 1 = Not at all; 2 = A little; 3 = Quite a bit; and 4 = A lot. Total scores for each domain are summed and divided by the total number of completed question responses. The overall QoL item ranges from 1 to 10. Lower scores indicate a higher QoL.

- Patient Interviews: Patients will be asked to participate in the qualitative interviews. The interviews will occur during screening and/or after completion of blinded treatment. The sample size was elected to be in line with best practice recommendations for cognitive debriefing of existing measures to provide evidence of content validity. Participants recruited for qualitative interviews will match the main inclusion and exclusion criteria found in the trial protocol (BCRL patients that have at least 6 months and no more than 15 years since the most recent type of breast cancer related surgery, have unilateral upper arm lymphedema no greater than 4 years).

The interviews will begin with concept elicitation using a set of open-ended questions that ask the patients to spontaneously identify the BCRL symptoms and daily activity impacts they experience. These data will be compared with the content of the existing instruments to determine whether they are complete and relevant in this target population.

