## **21. STATISTICS**

A statistical analysis plan (SAP) will be written that will describe, in greater detail, the analyses to be performed. The sections below provide a summary of the general approach to the analysis. The analysis is consistent with the study design and objectives. Note that this study is not hypothesis testing but rather hypothesis-generating, and thus conclusions regarding outcomes will not be based on inferential tests but rather descriptive outcomes, magnitude of treatment effects, and a preponderance of evidence regarding the risk-benefit profile of LYT-100.

As this study is hypothesis-generating, we will calculate effect sizes (Cohen's D, a standardized difference between the treatment arms) for efficacy and other endpoints as the data warrant. These values may be used to estimate sample sizes and/or power estimates for future clinical studies of LYT-100 in this population.

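### Appendix 3 scores a mostly blank LYMQOL domain as 0, better than the best possible score of 1; Section 17 has no such rule and gives the overall QoL item a different range

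*Combined protocol and SAP*

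**What the plan says.** **Item scale.** Section 17: "Each item is scored as 1 = Not at all; 2 = A little; 3 = Quite a bit; and 4 = A lot". Appendix 3 prints the same 1 to 4 codes, so lower is better for the domains.

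**Domain score in Section 17.** "Total scores for each domain are summed and divided by the total number of completed question responses". It states no minimum number of answers.

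**Domain score in Appendix 3.** A blank or not-applicable item is given 0, and the sum is divided by the number of questions answered. Then: "If >50% of questions per domain are not answered this cannot be calculated and =0".

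**Overall item.** Section 17: "The overall QoL item ranges from 1 to 10. Lower scores indicate a higher QoL". Appendix 3: "Overall quality of life (Q21) is scored as the value marked by the patient", on a printed line from 0 (Poor) to 10 (Excellent).

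**Use of the scores.** Section 21.7, on the visual analog scales and the two QoL questionnaires: "Both an MMRM and descriptive statistics will be used to describe the outcomes over time, considering each of their respective domains". Section 21 adds Cohen's D, "a standardized difference between the treatment arms) for efficacy and other endpoints as the data warrant", and says: "These values may be used to estimate sample sizes and/or power estimates for future clinical studies".

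**The concern.** A domain that cannot be scored should be missing. Appendix 3 instead gives it a number, and that number lies outside the scale on the favourable side. At a follow-up visit it reads as an improvement larger than any patient could achieve. At baseline it reads as a later worsening that did not happen. The arm with more incomplete forms is shifted.

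Section 17 does not carry the rule, so a programmer working from Section 17 and one working from Appendix 3 would derive different values from the same form. The overall item has a range conflict as well. Its direction is also unclear: the sentence saying that lower is better directly follows that item, although the form runs the other way.

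The study tests no hypotheses, so no error rate is at risk. What is at risk is the size of the estimated effect, which Section 21 makes the basis for conclusions and possibly for sizing later trials.

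**Working it through.** The plan gives no figure to reproduce: there is no sample-size calculation, no LYMQOL standard deviation and no rate of incomplete forms. The check is a comparison of the scoring rules, followed by arithmetic on labelled assumptions.

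**1. Range of a valid score.** Items take the values 1 to 4, so a mean of answered items lies in [1, 4]. The value 0 is 1 point below the best attainable score.

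**2. When the rule applies.** With m items in a domain, more than 50% unanswered means at least floor(m/2) + 1 blanks. Item counts are from Appendix 3.

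| Domain | Items | Blanks that trigger 0 |
|---|---|---|
| Function | 10 | 6 |
| Appearance | 5 | 3 |
| Symptoms | 6 | 4 |
| Mood | 6 | 4 |

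**3. Same answers, two scores.** Suppose 2 of 5 Appearance items are answered, both 3. Section 17 gives (3 + 3)/2 = 3.0; Appendix 3 gives 0. Suppose 2 of 6 Symptoms items are answered, both 4. Section 17 gives 4.0, the worst score; Appendix 3 gives 0.

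**4. The blank-item rule alone does no harm.** Because the divisor is the number answered, a blank scored 0 adds nothing to the sum and nothing to the divisor. The problem is confined to the 50% rule.

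**5. Largest possible error in one patient.** From a baseline of 2.0, the largest true improvement is 2.0 − 1 = 1.0. The rule records 2.0 − 0 = 2.0.

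**6. Effect on the arm comparison.** From the protocol: about 50 patients randomized 1:1, so n = 25 per arm. Assumed: a true score b of 1.5 to 2.5 at both visits for the affected patient, an SD of change s of 0.4 to 0.8, no treatment effect, and zeros at follow-up in one arm only.

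For k zero-coded patients:

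- mean shift = k·b/25
- affected-arm variance v = [(24 − k)·s² + (k(25 − k)/25)·(b² + s²/(25 − k))]/24
- pooled SD = √((v + s²)/2)
- d = shift / pooled SD

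| k | b | s | Shift | v | Pooled SD | False d |
|---|---|---|---|---|---|---|
| 1 | 1.5 | 0.8 | 0.06 | 0.704 | 0.820 | 0.073 |
| 1 | 2.0 | 0.6 | 0.08 | 0.506 | 0.658 | 0.122 |
| 1 | 2.5 | 0.4 | 0.10 | 0.404 | 0.531 | 0.188 |
| 2 | 1.5 | 0.8 | 0.12 | 0.761 | 0.837 | 0.143 |
| 2 | 2.5 | 0.4 | 0.20 | 0.626 | 0.627 | 0.319 |

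The variance formula includes the inflation that the 0 itself causes, so these d values are not overstated by ignoring it.

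**7. Does a baseline-adjusted model remove it?** No. As a stand-in for the MMRM, ANCOVA at one visit was simulated 4,000 times with no true effect. Coding one patient 0 instead of missing moved the treatment difference by about 0.06, 0.08 and 0.10 for b = 1.5, 2.0 and 2.5, in line with the simple shift.

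**8. Overall item.** Section 17 gives 1 to 10; Appendix 3 gives 0 to 10. The ranges disagree on any reading. If the sentence on lower scores covers this item, it contradicts the Poor-to-Excellent anchors. If it covers only the domains, Section 17 leaves the item's direction unstated.

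**The case against.** The best defence is that 0 was meant as a code for missing. The note says the score cannot be calculated, no valid answer is 0, and at item level the same note already uses 0 for non-response without harm. That is probably the intent. But the text assigns a value, no passage calls it missing, and at domain level nothing neutralises it as the divisor does for items.

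Second, Section 21.2 lets the SAP supersede the protocol's methods, and a SAP could settle the point. That stands as a limit on what can be claimed: the protocol does not prove that the 0 would reach the model. The combined document, however, contains no other LYMQOL scoring text, so the SAP author has only these two passages to work from.

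Third, Section 17 points to Appendix 3 and may be read as a summary, so its silence on the threshold is an omission and not a rival rule. That is fair. It softens the conflict over domain scoring, but it does not touch the 0 itself or the range conflict for the overall item.

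Fourth, the impact is small and rests on assumptions. LYMQOL is one of many secondary measures, nothing suggests that incomplete forms will differ by arm, and completeness checks under Section 20.2 might expose an out-of-range 0. The upper figure of 0.32 needs two mostly blank domains in one arm, none in the other, and the extreme assumed inputs. All of this is right, and it limits the severity without making the rule correct.

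**Conclusion.** The concern holds. As written, Appendix 3 turns a mostly unanswered domain into a score better than the best valid one, and nothing in the protocol keeps that value out of the domain analyses or effect sizes. Section 17 and Appendix 3 also disagree on the range of the overall item.

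The false d of 0.07 to 0.19 for one patient, or 0.14 to 0.32 for two in the same arm, is illustrative. It depends on assumed true scores and SDs and on zeros falling in one arm only. How often the rule would be triggered cannot be told from the documents. The answers recorded on the form are unaffected, so the harm is a wrong derived value that can be corrected. It should be fixed before analysis, but it does not threaten the trial.

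**What to change.** Put one scoring rule in Section 17, the Appendix 3 note and the SAP:

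- A domain score is the mean of its answered items. Blank and not-applicable items are left out of both the sum and the divisor.
- If more than 50% of a domain's items are unanswered, the domain score is missing at that visit and is never set to 0.
- Domain scores run from 1 to 4, lower is better.
- The overall item (Q21) runs from 0 to 10, higher is better, as printed on the form.

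The cost is a few sentences in each place and a matching line in the derivation program. No new data are needed, and any scores already derived can be recomputed from the raw items.
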